146 (heretofore referred to as “hotel”). Enrollment in the Pilot Study will proceed with the goal of
147 completing 1-3 participants. This admission will be up to 2 days will be in a hotel/rented house.

148 **1.3.1 Recruitment and Screening**

149 Participants will be recruited from the UVa Center for Diabetes Technology registry, social media
150 advertisements, physician/health care provider contacts at diabetes clinics in Virginia. Potential
151 participants will be informed of the study and will be encouraged to ask the study team questions
152 about their study participation. Participants will provide written informed consent. The
153 screening visit may be performed by telephone, video conferencing or in person.

154 **1.3.2 CGM Data Collection**

155 Following study enrollment, participants will be trained in use of the Dexcom G6 system,
156 provided with adequate study supplies and have a Dexcom sensor placed. This training may be
157 completed via video conferencing, with supplies sent to the participant in advance of the call.
158 This study visit will be followed by 4 weeks of CGM and pump data collection at the participant’s

CLINICAL PROTOCOL

159 home/usual routine. Participants will be asked to have breakfast and dinner at approximately
160 the same time at least 4-5 times per week during this period.

161 Participants will then be randomized to the order that they experience the three controller
162 approaches (for 24 hours each): 1) without the meal anticipation module and without
163 carbohydrate announcement (FCL), 2) with the meal anticipation module on and without
164 carbohydrate announcement (FCL+), or 3) without the meal anticipation module on and with
165 carbohydrate announcement (HCL). This will be performed using three permuted blocks of 6.

166 **1.3.3 Study Hardware/Software**

167 The study itself will involve use of the DiAs prototyping platform (MAF 2109), connected to a
168 Tandem t:AP research pump and a Dexcom G6 sensor, and implementing RocketAP with or
169 without the meal anticipation module. Upon arrival at the hotel, participants will be instructed
170 in how to use the Tandem research pump as well as the UVa AP system, including stopping the
171 system and bolusing for food.

[figure not shown]
172 **1.3.4 Timing of UVa Artificial Pancreas Use**

173 Upon arrival to hotel, participants will have a 12+ hour stabilization period. The participant will

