- 345 ○ Loss of consciousness

CLINICAL PROTOCOL

- 346 • Surgical history
347 • Allergies
348 • Concomitant medications
- 349 3. Physical Examination – If performed remotely, a historical history and physical report
350 within 18 months of screening appointments may be used but is not required for
351 eligibility. If vitals are not available, may include self-reported weight and height.
- 352 ○ Weight
353 ○ Height
354 ○ Blood pressure
355 ○ Temperature
356 ○ Heart Rate
- 357 4. Screening Labs
- 358 ○ Hemoglobin A1c point of care
359 ○ Urine or serum pregnancy test for all women of childbearing potential
- 360 Screening procedures will last approximately 1-2 hours. Screening can be performed via
361 telephone or video conference. Once all results of the screening evaluations are available, a
362 decision will be made to determine the participant’s eligibility for the study or if one or more part
363 of the screening will have to be repeated. If at the first screening or repeat screening an
364 exclusionary condition is identified, the participant will be excluded from participation with
365 follow up and referred to their primary care physician as needed. The study physician may elect
366 to rescreen participants if their clinical situation changes. Notably, screening is for determining
367 study eligibility. Once participants are found to be eligible, they can begin their data collection
368 phase as noted in Pilot Participants or Main Study.
- 369 **3.7 Demographic Data Survey**
- 370 The Demographic Data Survey will be electronically administered once eligibility has been met.

371 **Chapter 4 Randomization**

372 Participants will receive the three different experimental condition (FCL, FCL+, HCL) in random
373 order as described below.

374 **4.1 Pilot Study Participants**

375 Pilot participants will not be randomized but will only use the meal anticipation module with an
376 experimental meal without carbohydrate announcement and a study meal that is later than the
377 usual entrained timing.

378 **4.2 Main Study Participants**

379 Once eligibility is met and the Data Collection Phase (CGM/Meal Entrainment) period is
380 complete, the participant may continue to randomization. Screening failures and study dropout
381 participants may be replaced. Randomization will determine the order of the Study Controller
382 Sessions, with potential order as shown in Figure 1. Randomization will occur via permuted
383 blocks of 6.

CLINICAL PROTOCOL

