443 settings due to recurring hypo- or hyperglycemia. No pump settings changes can occur during
444 closed loop testing.

445 **Chapter 6 Pilot Study**

446 In order to optimize the flow of the study visits during the Main Study, we will perform a Pilot
447 Study with up to three pilot participants at a local hotel or rental house. Participants and staff
448 will adhere to the COVID -19 Mitigation Plan as outlined in Section 10.3. The duration of the pilot
449 admission will be approximately 24 hours with the intent of collecting appropriate safety data.
450 Pilot study participants are eligible to enroll in the Main Study.

451 **6.1 Data Collection Phase**

452 Participants will wear the study CGM at home for approximately 28 days. If currently using a
453 Dexcom G6, up to 30 days of data may be obtained from the participant's personal CGM and
454 pump. The investigators may still ask G6 users to complete this run-in phase at their discretion.

455 **6.2 Qualifications and Role of the Staff**

456 For the pilot study, there will be at least two study staff present at all times at the study site, at
457 least one of whom will be clinical staff (e.g. nurse, physician, nurse practitioner). There will be a
458 physician available either on-site or off-site within an approximate 20-minute drive at all times.
459 In addition, one of the study medical physicians and one senior engineer will be on call during
460 the entire admission. Glucagon for the emergency treatment of hypoglycemia will be available
461 on-site.

462 **6.3 Pre-Admission Check-In Visit**

463 Pilot participants will be contacted by the study team approximately 24-48 hours prior to the
464 hotel admission to verify the following information:

- 465 • Inquire about any changes to the participant's medical history
- 466 • Study equipment (e.g. CGM and activity tracker) initiation has occurred
- 467 • Determine pump profile(s) the participant uses on certain days
- 468 • New CGM sensor has been placed approximately 24-72 hours prior to admission for
469 proper warm-up
- 470 • Verify with the participant that the goal CGM reading at time of arrival is less than 200
471 mg/dL; this may require contact with the study physician prior to arrival on the day of the
472 study visit
- 473 • Should any concerns regarding medical history, pump information, or unforeseen issues
474 arise, the admission will be cancelled for that participant at the discretion of the
475 investigator

CLINICAL PROTOCOL

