566 mg/dL; this may require contact with the study physician prior to arrival on the day of the
567 study visit
- 568 • Should any concerns regarding medical history, pump information, or unforeseen issues
569 arise, the admission will be cancelled for that participant at the discretion of the
570 investigator

571 **7.5 Admission Check-In**

572 Day 0 Arrival

573 Participants will arrive at the hotel on the first day of the admission. The study team will inquire
574 about any changes to the participant's medical history. Any changes to medical history will be
575 communicated to the medical physician to ensure continued eligibility and participation.

576 A new CGM sensor will be placed if the sensor has not been changed within the last 24-48 hours.

577 Participants will be provided unstructured dinner (no meal-time restrictions). Participants are on
578 their home devices overnight and, therefore, no study staff are required to be present.

579 Day 1 Morning

580 The study team will perform vital signs. The subject's CGM reading, and ketone concentration
581 will be recorded. In the event that the participant's CGM reading is not between 80-250 mg/dL
582 or ketone concentration is ≥ 0.6 mmol/L prior to initiation of the UVa artificial pancreas system,
583 the study physician may recommend additional insulin dosing according to the participants' usual
584 doses. Study physician may elect to cancel participant's participation in the hotel admission if
585 concerned about their medical safety. This participant will not be replaced. A urine pregnancy
586 test will be collected for female participants of childbearing age within 24 hours prior to

CLINICAL PROTOCOL

587 transitioning to the AP Controller. The test must be negative for the participant to continue with
588 the study.

589

590 The participant's home insulin pump will be discontinued, and the study insulin pump will be
591 initiated. The insulin site will be changed and the participants may use the Tandem t:AP2 pump
592 without the DiAs platform for basal delivery until transition to AP. The study team will ensure the
593 proper function of the CGM, insulin pump, and activity tracker.

594 The CGM used in the study is FDA-approved for the non-adjunctive measurement of blood
595 glucose (i.e. the CGM reading can be used for insulin dosing decisions). The CGM readings will be
596 the primary source of blood glucose values. There are no protocol fingerstick blood glucose

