597 measurements other than at times of CGM calibration (if necessary) and if directed by the study
598 team. Fingerstick blood glucose measurements may be taken whenever participants experience
599 symptoms, if the CGM glucose is suspected to be erroneous, or any time the participant would
600 like to be reassured. Glycemic Treatment Guidelines to be used during the hotel admission are
601 defined in a separate document.

602 **7.6 Study Meals**

603 Participants will eat structured study meals during the admission, with the same amount of
604 carbohydrate, protein, and fat for the same meals (breakfast, lunch, dinner) on different days
605 (days 1, 2, and 3). Meal content may differ on the same day. The dinners will occur approximately
606 2 hours after the time that is usual for the participant from the Data Collection Phase (CGM/Meal
607 Entrainment period, defined as the median time of recorded meals between 6 and 8pm). The
608 breakfasts will occur at approximately the time that is usual for the participant from the Data
609 Collection Phase (CGM/Meal Entrainment period, defined as the median time of recorded meals
610 between 5am and 8am), and the lunches will occur at approximately noon (see Figure 2).

611 Participants will consume approximately 30-90 grams of carbohydrates at each meal. The study
612 participant will determine the quantity of carbohydrates in each meal and will enter this
613 information into the insulin pump with staff supervision during HCL. Staff will separately record
614 the calculated carbohydrate count at each meal. The carbohydrate content of the system will
615 only be announced during the HCL Controller period. During HCL, correction doses of insulin will
616 also be calculated at the time of meals. During FCL and FCL+, study staff will be monitoring the
617 closed-loop system as usual to identify insulin administration in the setting of postprandial
618 hyperglycemia. Staff will continue to follow the Glycemic Treatment Guidelines detailed in
619 Chapter 8. Snacks with carbohydrates will not be allowed unless for the treatment of low blood
620 sugars. Non-carbohydrates snacks are allowed throughout the protocol. Blood glucose levels will

CLINICAL PROTOCOL

621 be followed via continuous glucose monitor and glucose values will be managed by the AP system
622 as usual.

623 **7.7 Admission Activities**

624 Participants will be free to engage in low-intensity activity (i.e. walking) during the hotel

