1095 For security and confidentiality purposes, subjects will be assigned an identifier that will be used
1096 instead of their name. Protected health information gathered for this study may be shared with
1097 the third-party collaborators. De-identified subject information may also be provided to
1098 collaborators involved in the study after the appropriate research agreement has been executed.

1099 **Chapter 13 Statistical Consideration**

1100 **13.1 Statistical and Analytical Plans**

1101 We will conduct a paired comparison of outcomes between each admission (FCL vs. FCL+, HCL vs
1102 FCL, and FCL+ vs HCL), using Student paired t-test for percent in ranges and average CGM, and
1103 Wilcoxon test for overtly non normally distributed residuals (which often occur with outcomes
1104 such as % time below 70mg/dL, as well as 50, or 60mg/dL, and % time above 250mg/dL).
1105 Furthermore, we will use repeated measure ANOVA 3x2 with within factors and contrasts (to
1106 differentiate the repeated measures) if covariates are deemed necessary in the analysis.

1107 We do not plan to correct for multiple comparisons.

1108 We do not expect substantial missing values in this highly supervised study, but if more than 3
1109 subjects have one or more missing admissions, we will consider switching from RANOVA to mixed
1110 model repeated measures.

1111 **13.2 Statistical Hypotheses**

1112 The hypotheses for the primary outcome are:

1113 a. Null Hypothesis: There is no difference in the time spent in the 70-180mg/dL range within the
1114 breakfast postprandial period (mealtime to mealtime+5h) between FCL and FCL+ (without and
1115 with anticipation respectively)

1116 b. Alternative Hypothesis: There is a difference in the time spent in the 70-180mg/dL range within
1117 the breakfast postprandial period (mealtime to mealtime+5h) a between FCL and FCL+ (without
1118 and with anticipation respectively).

1119 **13.3 Design and Randomization**

1120 The main study is itself a pilot study to assess glycemic responses to three different approaches
1121 to insulin dosing for carbohydrate ingestion, with different approaches to the RocketAP system
1122 (1) without the meal anticipation module and without carbohydrate announcement (FCL), 2) with
1123 the meal anticipation module on and without carbohydrate announcement (FCL+), or 3) with the
1124 meal anticipation module on and with carbohydrate announcement (HCL), in random order).

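### The primary FCL+ versus FCL paired test has no period term; adding one is a minor, cheap efficiency gain, not the repair of an invalid test

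*Combined protocol and SAP*

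**What the plan says.** **Test.** Section 13.1 compares the three conditions in pairs: "FCL, and FCL+ vs HCL), using Student paired t-test for percent in ranges and average CGM, and". It switches to a Wilcoxon test when residuals are plainly non-normal. A 3x2 repeated-measures ANOVA is held in reserve in case covariates are thought necessary; its second factor is not defined. A mixed model is only to be considered, and only if more than three subjects miss a session. Period, day and sequence are not named as model terms anywhere.

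**Order.** Three 24-hour sessions follow one another in random order. Section 1.3.2 says: "carbohydrate announcement (HCL). This will be performed using three permuted blocks of 6". Section 13.3 also specifies permuted blocks of 6, without a count. Three blocks cover 18 participants; the target of 36 needs six.

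**Losses.** Section 4.2 says of screening failures and dropouts: "participants may be replaced. Randomization will determine the order of the Study Controller". Section 7.5, on an admission cancelled on Day 1, says: "concerned about their medical safety. This participant will not be replaced". Section 12.2 leaves the use of withdrawn participants' data to the study team.

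**Conditions during the stay.** Section 5.3.3 states "No pump settings changes can occur during" closed-loop testing. Section 7.6 fixes meal content across days and adds: "Snacks with carbohydrates will not be allowed unless for the treatment of low blood" sugar. Section 7.5 covers the devices: "The insulin site will be changed and the participants may use the Tandem t:AP2 pump", and "A new CGM sensor will be placed if the sensor has not been changed within the last 24-48 hours".

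**The concern.** Randomising the order of sessions protects the comparison of means from drift over the stay. It does not remove drift from the individual differences. A participant who has FCL on the first day and FCL+ on the third carries two days of drift in one direction; a participant with the reverse order carries it in the other. A paired t-test reads that predictable spread as random error. The standard error is then too large, the interval too wide, and a real benefit of meal anticipation easier to miss. The design already records what is needed to take this variation out, but the analysis does not use it.

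**Working it through.** **Inputs.** From Section 13.4: N = 36, effect 11 points, SD 22. From Section 13.2: a two-sided alternative. Assumed: alpha 0.05 (not stated); 22 is the SD of the paired difference; all six orders are used with six participants each (Figure 1 is not available); drift is linear at g TIR points per day (no size is given).

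**Step 1: the plan's own figure.** d = 11/22 = 0.5 and the noncentrality is 0.5 × √36 = 3.0. With 35 df, power is 83.1%. The detectable d is 0.480 at 80% power and 0.618 at 95% (normal approximation 0.467 and 0.601). The plan's approximate 0.5 and 0.6 are reproduced.

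**Step 2: what drift does.** The difference for participant i is the treatment effect, plus the period effect of the FCL+ day minus that of the FCL day, plus error. Over the six orders, the FCL+ day minus the FCL day equals +1, +2, +1, −1, −2, −1.
- The sum is 0, so the mean difference is unbiased.
- The mean square is (1+4+1+1+4+1)/6 = 2, so the variance of the differences becomes 22² + 2g².

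**Step 3: power and type I error.** Simulation, 40,000 trials per scenario; the ranges are over repeated runs.

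| Drift per day | √(484 + 2g²) | Paired power | Period-adjusted power | Paired type I error |
|---|---|---|---|---|
| 0 | 22.0 | 83% | 83% | 5.0% |
| 2 | 22.2 | 83% | 83% | 4.7–5.0% |
| 5 | 23.1 | 80–81% | 83% | 3.8–4.2% |
| 10 | 26.2 | 71–72% | 83% | 2.0–2.1% |

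The mean estimated paired standard error is 3.64, 3.67, 3.83 and 4.35. The true one stays near 22/6 = 3.67, so at 10 per day the interval is about 19% too wide (4.35/3.67 = 1.19). Period adjustment leaves 33 df. With no drift, exact power is then 82.94% against 83.07%, a cost of about 0.1 point. Break-even is at about 1 point per day.

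**Step 4: reading of the SD.** If 22 is a per-session SD with within-person correlation ρ, the SD of differences is 22√(2(1−ρ)), which is 22 at ρ = 0.5.
- ρ = 0.3 (SD 26.0): paired power 70/69/66/59% at drift 0/2/5/10, against 69% adjusted.
- ρ = 0.7 (SD 17.0): 96/96/95/88%, against 96%.
- If 22 is the SD of differences and already contains the drift, the residual SD is √(484 − 2g²) = 22.0/21.8/20.8/16.9. Paired power is then 83/83/84/89%, against 83/84/87/97% adjusted.

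**Step 5: unbalanced orders.** Over all 7,140 ways to lose 3 of 36, the mean bias of the unadjusted estimate is zero. The mean absolute bias is 0.0589g, or 0.1, 0.3 and 0.6 points at 2, 5 and 10 per day. If all three losses come from the order FCL–HCL–FCL+, the bias is −6g/33, or −0.9 and −1.8 points at 5 and 10 per day. Under random loss that has probability 20/7,140 = 0.28%.

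**The case against.** The strongest reply is that this hardly matters. No document reports any drift, and the design limits it: a stabilisation period, fixed pump settings, identical meals, restricted snacks, low-intensity activity and staff supervision. The only scenario with a large loss, 10 points per day, means a 20-point shift from first to third session, almost twice the 11-point target. Section 13.3 calls the main study itself a pilot, and Section 13.4 says its size rested on feasibility. All of this stands, and it makes the point minor.

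Four stronger readings are tempting, and the documents do not support them.

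- *The planned test is invalid.* With balanced orders it is unbiased and, if anything, conservative.
- *Infusion site and sensor age with session number in everyone, so drift must be expected.* Section 7.5 shows a site change on Day 1 and a sensor rule at arrival. Nothing forbids a later site change, and Chapter 8 provides for considering one. Sensors are placed ahead of admission to warm up and last 10 days.
- *Withdrawals will bias the result.* The replacement rules leave balance unguaranteed, but the expected bias from random loss is zero.
- *The Wilcoxon fallback should also go, in favour of a period-adjusted permutation test.* With heavy-tailed errors (t, 3 df) Wilcoxon power is about 97/96/94/84% at drift 0/2/5/10, against about 85–86% for the permutation test. The permutation test, which swaps FCL and FCL+ with HCL held in place, would also need all six orders, which cannot be confirmed without Figure 1.

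One might also say that the contingent 3x2 ANOVA could carry period. It does not name period, and its trigger is a later judgement.

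**Conclusion.** The point holds as a minor efficiency improvement. The primary paired test ignores period in a design that randomises order. A positive result from balanced orders stands. The loss is negligible at or below about 2 TIR points per day, 2 to 3 power points at 5, and about 11 at 10; the drift that will occur is unknown. These figures rest on the assumed alpha, linear drift, six balanced orders and 22 as the SD of differences. Other readings of the SD change the level of power, but adjustment still helps only when drift is appreciable. Protection of the estimate if orders become unbalanced is a secondary benefit. Period adjustment does not deal with carry-over between consecutive sessions.

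**What to change.** Pre-specify one primary analysis in Section 13.1. For participants with both breakfast windows, regress the FCL+ minus FCL difference in TIR on two columns, one each for periods 2 and 3. Each column is the indicator that FCL+ fell in that period minus the indicator that FCL did. The intercept is the treatment effect, tested two-sided at 0.05 with a 95% interval and 36 − 3 = 33 df. With fully balanced orders the estimate equals the plain mean difference; only its standard error changes.

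Keep the unadjusted paired t-test as a sensitivity analysis, and keep the planned Wilcoxon test for overtly non-normal residuals.

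The cost is SAP wording, a few lines of code on data already held, and two degrees of freedom (about 0.1 point of power if there is no drift). It should be written in before results are seen, since adding it afterwards would be a post hoc choice.

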- 1157 5. Number of hypoglycemia events defined as at least two consecutive CGM values
1158 <70mg/dL or a hypoglycemia treatment (two events separated by less than 30 minutes
1159 are counted as one).

CLINICAL PROTOCOL

- 1160 6. Percent CGM time <70 mg/dL
- 1161 7. Percent CGM time between 80-140mg/dL
- 1162 8. Percent CGM time between 70-180mg/dL
- 1163 9. Percent CGM time >180 mg/dL
- 1164 10. Percent CGM time >250 mg/dL
- 1165 11. Units of insulin injected
- 1166 12. Area under the curve when accounting for starting BG
- 1167 13. Low Blood Glucose Index
- 1168 14. High Blood Glucose Index
- 1169 15. CGM coefficient of variation

1170 **13.6 Safety Analyses**

1171 We will assess for the system's functionality, including the ability of the system to run its code
1172 without error (delivering insulin safely, as planned), as well as its ability to avoid low BG <70
1173 mg/dL.

1174 **13.7 Baseline Descriptive Statistics**

1175 Baseline demographic and clinical characteristics of the cohort of all randomized participants will
1176 be summarized in a table using summary statistics appropriate to the distribution of each
1177 variable. Descriptive statistics will be displayed overall and by treatment group.

1178 Will include:

- 1179 1. Age
- 1180 2. HbA1c
- 1181 3. Gender
- 1182 4. Race/ethnicity
- 1183 5. CGM use before enrollment
- 1184 6. AID use before enrollment

CLINICAL PROTOCOL

1185 7. Diabetes duration

1186 8. BMI

1187 9. Total Daily Insulin

1188 **13.8 Device Issues**

1189 The following tabulations and analyses will be performed during time on the UVa AP systems to
1190 assess device issues:

1191 1. Device malfunctions requiring study team contact and other reported device issues

1192 2. % time CGM data available

1193 3. % time with closed loop control

1194 **Chapter 14 Data Collection and Monitoring**

1195 **14.1 Case Report Forms and Device Data**

1196 The study data are collected through a combination of case report forms (electronic and paper)
1197 and electronic device data files obtained from the software and individual hardware
1198 components. These electronic device files and electronic CRFs are considered the primary source
1199 documentation.

1200 When data are directly collected in electronic case report forms, this will be considered the
1201 source data. Records will be maintained in accordance with ICH E6 and institutional regulatory
1202 requirements for the protection of confidentiality of participants.

1203 **14.2 Study Records Retention**

1204 Study documents should be retained for a minimum of 2 years after the last approval of a
1205 marketing application in an ICH region and until there are no pending or contemplated marketing
1206 applications in an ICH region or until at least 2 years have elapsed since the formal
1207 discontinuation of clinical development of the investigational product. These documents should
1208 be retained for a longer period, however, if required by local regulations. No records will be
1209 destroyed without the written consent of the sponsor, if applicable. It is the responsibility of the
1210 sponsor to inform the investigator when these documents no longer need to be retained.

1211 **14.3 Protocol Deviations**

1212 A protocol deviation is any noncompliance with the clinical trial protocol, Good Clinical Practices
1213 (GCP), or procedure requirements. The noncompliance may be either on the part of the
1214 participant, the investigator, or the study site staff. As a result of deviations, corrective actions
1215 may be developed by the site and implemented as appropriate. Major deviations will be reported
1216 to the IRB-HSR within 7 calendar days of when the study team becomes aware of the event.

CLINICAL PROTOCOL

1217 **Chapter 15 Ethics/Protection of Human Participants**

1218 **15.1 Ethics Standard**

1219 The investigator will ensure that this study is conducted in full conformity with Regulations for
1220 the Protection of Human Participants of Research codified in 45 CFR Part 46, 21 CFR Part 50, 21
1221 CFR Part 56, and/or the ICH E6.

1222 **15.2 Institutional Review Boards**

1223 The protocol, informed consent form(s), recruitment materials, and all participant materials will
1224 be submitted to the IRB for review and approval. Approval of both the protocol and the consent
1225 form must be obtained before any participant is enrolled. Any amendment to the protocol will
1226 require review and approval by the IRB before the changes are implemented to the study. All
1227 changes to the consent form will be IRB approved; a determination will be made regarding
1228 whether previously consented participants need to be re-consented.

1229 **15.3 Informed Consent Process**

1230 **15.3.1 Consent Procedures and Documentation**

1231 Informed consent is a process that is initiated prior to an individual's agreement to participate in
1232 the study and continues throughout the individual's study participation. Extensive discussion of
1233 risks and possible benefits of participation will be provided. Consent forms will be IRB approved
1234 and the participant will be asked to read and review the document. The investigator or their
1235 delegate will explain the research study to the participant and answer any questions that may
1236 arise. All participants will receive a verbal explanation in terms suited to their comprehension of
1237 the purposes, procedures, and potential risks of the study and of their rights as research
1238 participants. Participant will have the opportunity to carefully review the written consent form
1239 and ask questions prior to signing.

1240 The participant and the parent(s)/legal guardians will sign the informed consent document prior
1241 to any procedures being done specifically for the study. The consent forms may be signed
1242 electronically with the use of the HIPAA compliant version of DocuSign. A copy of the informed
1243 consent document will be given to the participant for their records. The rights and welfare of the
1244 participants will be protected by emphasizing to them that the quality of their medical care will
1245 not be adversely affected if they decline to participate in this study.

CLINICAL PROTOCOL

1246 **15.3.2 Participant and Data Confidentiality**

1247 The study monitor, representatives of the IRB or device company supplying study product may
1248 inspect all documents and records required to be maintained by the investigator, including but
1249 not limited to, medical records (office, clinic, or hospital) for the participants in this study.

1250 The study participant's contact information will be securely stored at the clinical site for internal
1251 use during the study. At the end of the study, all records will continue to be kept in a secure
1252 location for as long a period as dictated by local IRB and Institutional regulations.

1253 Study participant research data, which is for purposes of statistical analysis and scientific
1254 reporting, will be transmitted to and stored at the University of Virginia Center for Diabetes
1255 Technology. The study data entry and study management systems used by research staff will be
1256 secured and password protected. At the end of the study, all study databases may be de-
1257 identified and archived at the University of Virginia Center for Diabetes Technology.

